3.4.2 Inclusion Criteria

Subjects are required to meet the inclusion criteria presented in [Table 3.4.2-1](#).

Table 3.4.2-1 Inclusion Criteria	
1.	Male and female subjects between the ages of 18 and 70 years, inclusive.
2.	Diagnosis of Crohn's disease localized in the ileum and/or colon, with active mucosal inflammation and visible lesion(s), documented by centrally read ileocolonoscopy and a SES-CD ≥ 6 (≥ 4 for isolated ileal disease).
3.	Subjects who do not have an optimal response ^a (daily stool frequency > 3 and pain score > 1) to their current ongoing treatment of biologics (eg, first anti-TNF- α monoclonal antibody), immunosuppressants, low-dose steroids, or 5-ASA formulations.
4.	Subjects who are on stable Crohn's disease medications for at least 4 weeks.
5.	Subjects with a CDAI score between 180 and 450 points, inclusive.
6.	Subjects who are willing and able to follow the trial protocol and have signed informed consent.

^aThe minimum duration of prior treatment required for a subject to be considered as having a nonoptimal response includes completing at least the recommended induction regimen for approved biologics and/or treatment at a therapeutic dose for a stable duration that would be anticipated to result in improvement (ie, 12 weeks for azathioprine, 4 weeks for methotrexate). Prior treatment examples and their minimum durations can be found in [Appendix 4](#).

3.4.3 Exclusion Criteria

Subjects will be excluded if they meet any of the exclusion criteria in [Table 3.4.3-1](#).

Table 3.4.3-1 Exclusion Criteria	
1.	Females who are breast-feeding and/or who have a positive pregnancy test result prior to receiving IMP.
2.	Sexually active males or WOCBP who do not agree to practice 2 different methods of birth control or remain abstinent during the trial and for 30 days after the last dose of IMP. If employing birth control, 2 of the following precautions must be used: vasectomy, tubal ligation, intrauterine device, birth control pill, birth control implant, or birth control depot injection. A vaginal diaphragm, condom with spermicide, or sponge with spermicide may also be used as measures to prevent pregnancy, but must be used in combination with at least one of the previous methods.
3.	Subjects taking any nonsteroidal anti-inflammatory drugs that cannot be stopped or replaced.
4.	Use of prednisone or prednisolone > 30 mg/day or budesonide > 9 mg/day within 4 weeks prior to screening; or intravenous steroids within 4 weeks prior to screening.
5.	Subjects taking antithrombotic drugs.
6.	Subjects with symptomatic bowel stenosis, fistula, or stoma; or with more than 2 bowel resections.
7.	Subjects with short bowel syndrome.
8.	Subjects with known existing aortic aneurysm, or who are at risk for an aortic aneurysm, such as subjects with peripheral atherosclerotic vascular diseases, uncontrolled hypertension, certain genetic conditions such as Marfan syndrome and Ehlers-Danlos syndrome, and elderly subjects (over the age of 70).
9.	Subjects with known or suspected (family history, unexplained syncope) long QT syndrome or QTcF > 470 msec for females or > 450 msec for males at baseline.

Protocol 341-201-00004

Table 3.4.3-1 Exclusion Criteria

10.	Subjects with inadequate organ function, as follows: 
 • Serum creatinine $> 1.5 \times \text{ULN}$ • AST or ALT levels $> 1.5 \times \text{ULN}$ • Total bilirubin $> 1.5 \times \text{ULN}$. Elevated unconjugated bilirubin related to Gilbert's syndrome is allowed.
11.	Use of antibiotics (eg, metronidazole, rifaximin, tinidazole, ciprofloxacin, clarithromycin) within 15 days prior to screening or for greater than 2 months within the past year. A short course (maximum of 5 days) of antibiotics will be permitted during the trial, as needed, for indications other than Crohn's disease.
12.	Known hypersensitivity to quinolones or other significant adverse reaction to quinolones.
13.	Conditions or circumstances that could prevent completion of the trial according to the judgment of the investigator, including an uncontrolled comorbidity, heart condition, or dysfunction of any other organ; peripheral neuropathy; known arrhythmias, atrial fibrillation, or paroxysmal tachycardia; history of myasthenia gravis; history of drug or alcohol abuse, mental illness, or noncompliance with treatments or visits; or known immune-deficiency. ^a
14.	HIV infection, viral hepatitis, prior organ transplant, or malignant disease that is not in remission for at least 3 years, with the exception of basal cell carcinoma.
15.	Subjects who have used any investigational drug within 2 months prior to screening.
16.	Blood donation in the last 2 months.
17.	Use of inhibitors of UGT1A1 and UGT1A9 (eg, Silybin, diclofenac, mycophenolic acid, efavirenz, regorafenib) and BCRP (eg, Estrone, 17 β -estradiol, flavonoids, herb extracts, gefitinib, imatinib, tamoxifen, novobiocin, nelfinavir, ritonavir, dipyridamole, fumitremorgin C, Ko143, cyclosporine, curcumin, eltrombopag, omeprazole, ivermectin).
18.	Subjects with a history of treatment failure with 2 or more biologics. ^b
19.	Subjects with risk factors for tendon rupture (ie, psoriasis, ankylosing spondylitis, competitive athletes, renal failure, diabetes mellitus) or who have a history of tendon rupture and/or ongoing tendinopathy.
20.	Subjects with systolic blood pressure $> 150 \text{ mmHg}$ or diastolic blood pressure $> 90 \text{ mmHg}$.
21.	Subjects taking quinidine, procainamide, disopyramide, encainide, flecainide, sotalol, amiodarone, ibutilide, dronedarone, or propafenone.

BCRP = breast cancer resistance protein; HIV = human immunodeficiency virus; QTcF = QT interval corrected for heart rate by the Fridericia formula; WOCBP = women of childbearing potential.

^aSubjects that test positive for marijuana or for confirmed prescription medications (eg, opioid analgesics) may be permitted to be enrolled if they have no evidence of a substance use disorder. Allowance for subjects testing positive for marijuana or confirmed prescription medications at screening requires explicit approval from the medical monitor.

^bThe rationale for excluding subjects who have failed 2 or more biologics is due to the fact that they may represent an especially difficult-to-treat population (ie, medically refractory) that may not benefit substantially from fluoroquinolones and/or will likely need additional, more invasive treatment (ie, surgical resection).

Subjects must agree to restrictions as described in [Section 4](#).

Subjects excluded for drug or alcohol abuse are not eligible to be rescreened for participation in the trial. However, subjects excluded for other reasons may be rescreened at any time if the exclusion characteristic has changed. Subjects are permitted to be

Protocol 341-201-00004

rescreened 3 times. In the event that the subject is rescreened, a new ICF must be signed, a new screening number assigned, and all screening procedures repeated.

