4.1 Prohibited Medications

In vitro studies have shown that OPS-2071 is a substrate of breast cancer resistance protein (BCRP) transporters, UGT1A1 mainly and UGT1A9 partially. Hence, it is recommended to avoid concomitant use of BCRP inhibitors (eg, Estrone, 17 β -estradiol, flavonoids, herb extracts, gefitinib, imatinib, tamoxifen, novobiocin, nelfinavir, ritonavir, dipyridamole, fumitremorgin C, Ko143, cyclosporine, curcumin, eltrombopag, omeprazole, ivermectin) and UGT1A1 or UGT1A9 inhibitors (eg, Silybin, diclofenac, mycophenolic acid, efavirenz, regorafenib).

The following medications are prohibited:

- Use of prednisone or prednisolone > 30 mg/day or budesonide > 9 mg/day, or intravenous steroids, within 4 weeks prior to screening. Low-dose steroids may be tapered down during the trial, based on inflammatory biomarkers and the investigator's judgment.
- Antibiotics (eg, metronidazole, rifaximin, tinidazole, ciprofloxacin, clarithromycin) within 15 days prior to screening or for greater than 2 months within the past year. A short course (maximum of 5 days) of antibiotics will be permitted during the trial, as needed, for indications other than Crohn's disease.
- Nonsteroidal anti-inflammatory drugs
- Antithrombotic drugs:
 - Anticoagulants: heparin or warfarin (also called Coumadin), rivaroxaban (Xarelto), apixaban (Eliquis), edoxaban (Lixiana, Savaysa), betrixaban (Bevyxxa), bivalirudin, argatroban, and desirudin
 - Antiplatelet drugs: clopidogrel (Plavix) and aspirin (aspirin use of \leq 325 mg daily are permitted)

Protocol 341-201-00004

- Quinidine, procainamide, disopyramide, encainide, flecainide, sotalol, amiodarone, ibutilide, dronedarone, or propafenone

Subjects who increase dosages of baseline Crohn's disease medications or take a new therapy for Crohn's disease during the trial will be considered as treatment failures (nonresponders) in the efficacy analysis. These subjects are encouraged to stay in the trial for continuous data collection ([Section 3.8.3.2](#)).

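### BCRP/UGT inhibitors are barred at entry but only advised against during the 12 weeks of dosing; separately, exclusion criterion 5 omits the low-dose aspirin allowance given in Section 4.1

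*Protocol*

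**What the plan says.** **BCRP/UGT inhibitors.** Protocol Section 3.4.3, criterion 17, lists as an exclusion "Use of inhibitors of UGT1A1 and UGT1A9 (eg, Silybin, diclofenac, mycophenolic acid, efavirenz, regorafenib) and BCRP", followed by BCRP examples that include omeprazole, cyclosporine, 17β-estradiol, curcumin and herb extracts. Protocol Section 4.1 gives the reason: "In vitro studies have shown that OPS-2071 is a substrate of breast cancer resistance protein (BCRP) transporters, UGT1A1 mainly and UGT1A9 partially". From this it concludes that "it is recommended to avoid concomitant use of BCRP inhibitors" and of UGT1A1 or UGT1A9 inhibitors. That sentence comes before the list of prohibited medications. The list covers steroids, antibiotics, NSAIDs, antithrombotics and antiarrhythmics, and it does not include the inhibitors as a class.

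**Aspirin.** Criterion 5 reads "Subjects taking antithrombotic drugs", with no dose limit and no cross-reference. Section 4.1, under antithrombotic drugs, names "Antiplatelet drugs: clopidogrel (Plavix) and aspirin" and then adds that aspirin at or below "325 mg daily are permitted".

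**Link between the sections.** The text after the exclusion table says "Subjects must agree to restrictions as described in" Section 4.

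**The concern.** An exclusion criterion controls who enters, and eligibility is last verified on Day 1 before the first dose (Section 3.7.1.2). The reason for criterion 17 is a possible interaction, which can occur only while OPS-2071 is being taken, that is, during the 12 weeks that start on Day 1. The rule is therefore strict before the risk exists and soft while it does.

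Exposure is relevant to this compound. Section 1.3 expects fewer of the adverse reactions linked to systemic fluoroquinolones because bioavailability and systemic exposure are limited. Section 2.2 shows that repeat dosing in healthy subjects went up to 600 mg BID for at most 7 days, and this trial gives that dose for 12 weeks. A co-medication that might raise exposure needs a clear on-treatment rule. Section 3.8.3.2 names the need for a disallowed medication as one reason for stopping treatment, and a site cannot tell from a recommendation whether omeprazole counts as disallowed.

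For aspirin, the concern is only that different sites could handle the same low-dose user differently at screening, depending on which section they apply.

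**Working it through.** No figure in the plan bears on this point, so the check is a comparison of the current texts.

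**Inhibitors**

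1. *Entry.* Meeting any one exclusion criterion excludes the subject. Criterion 17 therefore binds at screening and on Day 1. It gives no washout period.
2. *On treatment.* Section 4.1 does not mention 12 weeks. The period follows from its reference to concomitant use together with the dosing period in Section 3.2. For that period the wording is a recommendation.
3. *Does this protocol use recommendation to mean a ban?* Section 4.2 suggests not. It has subjects advised to limit caffeine, but states that over-the-counter probiotics are not permitted. The two kinds of wording are kept apart within Section 4.
4. *Does agreeing to Section 4 make it binding?* Subjects agree to what Section 4 says. For these inhibitors it says that avoidance is recommended.
5. *Is any of the class caught elsewhere?* In part. Diclofenac is an NSAID and is prohibited on that ground. Cyclosporine or mycophenolic acid started for Crohn's disease would make the subject a treatment failure, but that is an analysis rule and does not stop co-administration. Omeprazole, 17β-estradiol, curcumin and herb extracts are not in the prohibited list.
6. *Result.* A subject who stops omeprazole in order to qualify may resume it after Day 1, and another may start it then, without breaching a binding rule.

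**Aspirin**

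1. By the protocol's own classification in Section 4.1, aspirin is an antithrombotic, so a literal reading of criterion 5 excludes a user of, say, 100 mg daily.
2. Section 4.1 allows that same use.
3. The exclusion table can carry an allowance when one is meant. Criterion 11 does so: "A short course (maximum of 5 days) of antibiotics will be permitted during the trial" for reasons other than Crohn's disease. Criterion 5 has no such words.
4. Asking subjects to accept the Section 4 restrictions adds obligations. It does not relax a criterion.

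**The case against.** **On the inhibitors.** Excluding users at entry and advising avoidance later is not a contradiction, and it can be a deliberate choice. The advice stands under a heading about prohibited medications. The basis is in vitro only, and Section 1.2 gives low solubility as the main reason for poor absorption. Advice is reasonable for foods and for broad groups such as flavonoids. Concomitant medications and adverse events are reviewed at the visits, and PK sampling, ECGs, laboratory tests and individual stopping rules would help to detect a problem. A ban also raises the question of how 17β-estradiol sits with the hormonal contraception accepted in criterion 2.

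Much of this stands, and it is why the point is minor. It does not explain why a drug thought serious enough to bar entry should be only discouraged once dosing begins. The contraception question already arises under criterion 17, so the proposed change does not create it.

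**On aspirin.** Section 4.1 is probably meant as the detail behind criterion 5. The Amendment 2 summary in Appendix 5 says that the term was changed to antithrombotic drugs in both sections, with further detail placed in Section 4.1. That reading is the likely intent. What remains is a missing cross-reference.

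**Stronger readings that the documents do not support.** A reader might infer that these inhibitors are the only class excluded at entry without an on-treatment ban. That does not follow: the steroid and antibiotic entries in Section 4.1 largely repeat pre-screening windows. A reader might also take Section 3.13 to show that breaches of concomitant-medication rules on treatment are deviations of unclear status. The example there concerns subjects enrolled in violation of such criteria, so it does not settle on-treatment use either way.

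**Conclusion.** Both differences are present in the current protocol text. The inhibitor rule is the main point: the binding restriction covers entry, and the period to which the stated concern applies has advice only. The aspirin point is editorial, with no consequence for results or safety.

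The size is minor. The documents give no interaction magnitude and no expected frequency of inhibitor use, so neither an exposure effect nor the share of subjects affected can be stated. It would go too far to conclude that subjects would have been harmed or that exposure would have risen materially. There is no effect on sample size, power, type I error or the primary analysis.

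The verdict assumes that exclusion criteria apply up to randomization and that a recommendation in Section 4 is not a prohibition. SAP Section 11 reports that the trial ended early with three randomized subjects, so the correction now matters mainly if this protocol text is reused.

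**What to change.** **Section 4.1.** Add medicinal and supplement inhibitors of BCRP, UGT1A1 and UGT1A9, matching criterion 17, to the prohibited list for the 12-week treatment period. Examples are omeprazole, 17β-estradiol, cyclosporine, and curcumin or herbal-extract supplements. Leave dietary flavonoids as advice.

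**Criterion 5.** Add the exception: except aspirin ≤ 325 mg daily (see Section 4.1).

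Both are wording changes that fit in one amendment and need no new procedures. The cost is some substitution of co-medication during treatment, for example a replacement for omeprazole, and some extra recorded deviations. The aspirin wording costs nothing beyond the edit.

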3.5 Endpoints

3.5.1 Primary Endpoint

The primary endpoint is the percentage of subjects who, at Week 12, achieve clinical remission (defined as a CDAI score < 150).

3.5.2 Secondary Endpoints

3.5.2.1 Secondary Efficacy Endpoints

The secondary efficacy endpoints are as follows:

- 1) The percentage of subjects with endoscopic response, defined as a reduction of the SES-CD by at least 50%, at Week 12.
- 2) Change from baseline in the SES-CD score.
- 3) The percentage of subjects with PRO-2 remission (defined as stool frequency \leq 3 times per day and abdominal pain \leq 1) at Week 12.
- 4) The percentage of subjects with clinical response, defined as at least a 25% decrease in the CDAI score, at Week 12.
- 5) The percentage of subjects who, at Week 12, achieve endoscopic remission (defined as a SES-CD score of 0 to 2; or a score of 0 to 4, with no individual subscore greater than 1).
- 6) The percentage of subjects with a decrease from baseline of \geq 100 points in the CDAI score.

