Appendix 3 Simple Endoscopic Score for Crohn's Disease (SES-CD)

Score	Meaning
0 - 2	Remission
3 - 6	Mild endoscopic activity
7 - 15	Moderate endoscopic activity
> 15	Severe endoscopic activity

Variable	SES-CD Values			
	0	1	2	3
Size of ulcers	None	Aphthous ulcers (diameter 0.1 to 0.5 cm)	Large ulcers (diameter 0.5 to 2 cm)	Very large ulcers (diameter > 2 cm)
Ulcerated surface	None	< 10%	10% - 30%	> 30%
Affected surface	Unaffected segment	< 50%	50% - 75%	> 75%
Presence of narrowings	None	Single, can be passed	Multiple, can be passed	Cannot be passed

Protocol 341-201-00004

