Appendix 4 Minimum Duration of Prior Treatments for Crohn's Disease

Prior Treatment ^a	Minimum duration of prior treatment required to be considered as having a nonoptimal response
Corticosteroids (eg Budesonide and Prednisone)	8 weeks
Aminosalicylates (eg Sulfasalazine and 5-ASA derivatives)	8 weeks
Thiopurines (eg 6-mercaptopurine and Azathioprine)	12 weeks
Methotrexate	12 weeks
Tumor necrosis factor-alpha inhibitors	8 weeks
Ustekinumab	8 weeks
Vedolizumab	8 weeks

^aList is not inclusive of all prior treatment options and investigator judgement is required.

Protocol 341-201-00004

Amendment Number:

Issue Date: 12 Apr 2019

PURPOSE:

The purpose of this protocol amendment is to modify the secondary and exploratory endpoints, as well as the schedule of assessments, and to remove the monthly telephone follow-up (and corresponding exploratory endpoint). In addition, exclusion criteria and stopping criteria were added, and inclusion criterion #3 and exclusion criteria #4, #12, #13, #14, and #19 were modified. Finally, other minor revisions were made and are listed below.

BACKGROUND:

Endoscopic remission is likely to be rare at 12 weeks; hence, this endpoint was placed amongst the general secondary endpoints. Since an endoscopic response by 12 weeks is possible, an endpoint was added to capture that data (by recording the change from baseline in SES-CD score). An endpoint was also added for a decrease from baseline of ≥ 100 points in the CDAI score because this is a common endpoint in Crohn's trial. The monthly telephone follow-up (and corresponding exploratory endpoint) was removed because this will have limited utility and may be confounded by many factors. Inclusion/exclusion criteria and stopping criteria were added and modified based on requests from the FDA. The other protocol revisions were made for clarity.

MODIFICATIONS TO PROTOCOL:

General Revisions:

- Moved the key secondary efficacy endpoint to the list of general secondary efficacy endpoints.
- Moved the third secondary endpoint of endoscopic response so that it is the first secondary endpoint.
- Added a secondary endpoint of “change from baseline in SES-CD score”.
- Added a secondary endpoint of “the percentage of subjects with a decrease from baseline of ≥ 100 points in the CDAI score”.
- Added “the percentage of subjects with” to the applicable secondary efficacy endpoints.

Protocol 341-201-00004

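### Endoscopic remission (secondary endpoint #5) is already met at entry by an isolated ileal subject scoring 1+1+1+1, so no change at Week 12 counts as remission (minor)

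*Protocol*

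**What the plan says.** Protocol 3.5.2.1 gives two routes to secondary efficacy endpoint #5, assessed at Week 12. One counts subjects who "achieve endoscopic remission (defined as a SES-CD score of 0 to 2". The alternative route is "or a score of 0 to 4, with no individual subscore greater than 1". The synopsis, Protocol 7.4.2 and SAP 8.2.1 use the same definition. None of them refers to the baseline score.

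Inclusion criterion 2 (Protocol 3.4.2) covers ileal and colonic disease and asks for a diagnosis "with active mucosal inflammation and visible lesion(s". The score threshold in the same criterion, on central reading, is "SES-CD ≥ 6 (≥ 4 for isolated ileal disease".

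Appendix 3 of the protocol gives four variables (ulcer size, ulcerated surface, affected surface, narrowings), each scored 0 to 3. Its severity table calls a total of 0 to 2 remission and 3 to 6 mild activity.

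SAP 8.2.2 makes a subject a non-remitter for escalating Crohn's medication, starting a new Crohn's therapy, or withdrawing early. It has no rule for subjects who already meet the definition at baseline.

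**The concern.** An endpoint described as achieving remission should not be attainable by a subject who enters the trial and does not change. For the other two remission endpoints, entry and remission are disjoint: CDAI entry is 180 to 450 against remission below 150, and symptom entry is stool frequency above 3 with pain above 1 against at most 3 and at most 1. For endoscopic remission, the ileal entry threshold of 4 touches the upper limit of the second route.

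The same endoscopic picture would then be active inflammation at screening and remission at Week 12. It would also be a non-response on secondary endpoint #1, because an unchanged score is a 0% reduction. The background to Amendment 1 gives the sponsor's expectation: "Endoscopic remission is likely to be rare at 12 weeks". With few true events, a small number of subjects counted this way could be visible in the reported percentages.

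**Working it through.** The documents give no rate, power or sample size for endoscopic remission, so there is no stated figure to reproduce. The check is whether the entry and remission rules can hold at once.

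**Step 1. Can every variable score 1?** Appendix 3 gives value 1 as:
- ulcer size: "Aphthous ulcers (diameter 0.1 to 0.5 cm"
- ulcerated surface: under 10%
- affected surface: under 50%
- narrowings: "Single, can be passed"

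Exclusion criterion 6 removes only symptomatic stenosis, so a silent, passable narrowing can enter. Aphthous ulcers supply the visible lesion. The total is 1 + 1 + 1 + 1 = 4, which meets the isolated ileal threshold.

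**Step 2. How many eligible ileal patterns meet the remission definition?** One segment with four variables scored 0 to 3 gives 4^4 = 256 patterns.
- Totals of 0, 1, 2 and 3 account for 1 + 4 + 10 + 20 = 35 patterns, so 256 − 35 = 221 meet entry (total ≥ 4).
- The 0-to-2 route overlaps with none of these.
- The second route needs every score ≤ 1. The largest possible total is then 4, reached only by 1+1+1+1.
- So 1 of the 221 eligible patterns qualifies. It is 1 of the 31 patterns that total exactly 4. No pattern totalling 5 or more qualifies.

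**Step 3. Can other disease locations be affected?** They enter at ≥ 6, above the cap of 4, so no.

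**Step 4. Size per subject.** With 60 per arm, one such subject adds 1/60 = 1.7 percentage points to that arm. In the pooled 600 mg and 300 mg group it adds 1/120 = 0.8 points.

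**Step 5. Direction (illustration with assumed inputs).** Let a share q of every arm enter and stay at 1+1+1+1, and let true remission among the rest be p. The observed rate is q + (1 − q)p, and the observed difference is (1 − q)(p1 − p0). Assume p0 = 5% and p1 = 15%, with 60 placebo and 120 pooled active subjects. Power is for an unadjusted two-sided 0.05 test: Φ[(d − 1.96·SE0)/SE1], where d is the observed difference, SE0 uses the pooled rate and SE1 the separate rates.

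| q | Placebo | Active | Difference | Power |
|---|---|---|---|---|
| 0 | 5.0% | 15.0% | 10.0 points | 50.5% |
| 2% | 6.9% | 16.7% | 9.8 points | 43.5% |
| 5% | 9.75% | 19.25% | 9.5 points | 36.0% |
| 10% | 14.5% | 23.5% | 9.0 points | 27.8% |

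For q = 0: SE0 = √(0.1167 × 0.8833 × (1/60 + 1/120)) = 0.0508, SE1 = √(0.05 × 0.95/60 + 0.15 × 0.85/120) = 0.0431, and (0.10 − 0.0995)/0.0431 ≈ 0.01, giving about 50.5%. Both rates rise and the difference narrows. None of q, p0 or p1 is in the documents.

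**The case against.** The case against giving this weight is strong on reach and consequence.

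- **Rarity.** The subject needs exactly 1 on all four variables, including a narrowing that is not judged symptomatic, together with a CDAI of 180 to 450 and the symptom criteria. The subject must then reach the Week 12 endoscopy without escalating Crohn's medication. This makes the case uncommon but does not exclude it. One pattern in 221 is a count of patterns, not a prevalence.
- **Meaning of subscore.** The term is undefined. If it meant a segment total, an ileal score of 4 would fail and the overlap would vanish. The Appendix 3 variable scores are the only subscores the documents show, so that is the natural reading, but the point depends on it.
- **Adjustment.** The planned model for #5 includes baseline SES-CD and disease location, so the comparison partly conditions on who these subjects are. It does not reclassify them, and the reported percentages stay affected.
- **Low weight of #5.** Endpoints #1 and #2 are measured against baseline and come first. Formal testing of #5 follows 3 + 3 + 2 tests on the primary endpoint and endoscopic response (the last 2 for 150 mg), then 4 each for #2, #3 and #4: 8 + 12 = 20 rejections, or 19 if endoscopic response has no pooled test. SAP section 11 adds that the planned analyses will not be performed, because the trial ended with three randomised subjects.

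These arguments limit the importance of the point; they do not remove the overlap.

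Stronger readings are tempting in three ways. A reader might infer a bias towards the drug; randomisation makes such subjects equally likely in every arm, so the expected effect is dilution. A reader might quote a large relative increase by setting one such subject against a handful of true remitters; the documents give neither number. A reader might conclude that a minimum fall of, say, 2 points is needed; no such threshold appears in the documents, and it would reject a subject who truly improved by one point, such as 2+1+1+0 falling to 1+1+1+0.

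**Conclusion.** The definition is wrong as written, in a minor way. An isolated ileal subject who enters at 1+1+1+1 and does not change is a remitter on endpoint #5, a non-responder on endpoint #1, and mildly active by the protocol's own severity table.

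The overlap at entry is confined to that one pattern in that one location. Its expected effect is to raise the reported remission rates in all arms and shrink the difference between them. The size is 1.7 percentage points per such subject in an arm of 60, with the number of such subjects unknown. The conclusion rests on reading individual subscore as a variable score and on the subject completing Week 12 without a medication change. With the trial stopped at three subjects, the practical value is in not carrying the definition into a later protocol.

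**What to change.** In the synopsis, Protocol 3.5.2.1 and 7.4.2, and SAP 8.2.1, add to the definition of endoscopic remission: *and a decrease from the baseline SES-CD score*. In the same places, state that *individual subscore* means the score of each SES-CD variable in Appendix 3.

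Any decrease is enough. A subject entering at 6 or more, or at 5, must already have fallen to finish at 4 or below, so the added words affect only ileal subjects who enter at a total of 4 and finish at 4.

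An alternative is to say that a subject who meets the definition at baseline is not counted without a decrease. The two rules agree for the 1+1+1+1 entrant. They part only for someone who enters at 4 in another pattern, such as 2+1+1+0, and ends at 1+1+1+1: requiring a decrease of everyone does not count that subject, and the alternative does. The sponsor should pick one; requiring a decrease of everyone is simpler to program.

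The cost is wording only. The observed remission rate may be slightly lower.
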